### 8.1 Aim I

The first study aim is to estimate the bias and precision of each of the following functional analytes, which will be measured for each target lesion by both vascuCAP™ and histopathology:

- a. Plaque lipid
- b. Plaque fibrosis
- c. Plaque inflammation
- d. Intra-plaque hemorrhage burden and confidence.
- e. Plaque vascular leak
- f. Calcification

For each of these functional analytes, three measurements will be evaluated for a total of 18 measurements per target lesion: volume in mm^3, and degree and uniformity both measured on a three-point ordinal scale. The same measurements will be taken via histopathology, where the volume of each analyte will be measured using the same units (i.e. mm^3); however, degree and uniformity are graded subjectively on histopathology by the pathologist.

We anticipate that each patient will have at least one target lesion and some patients, especially the PAD patients, will have two target lesions, on average. There will be no replicate measurements (i.e. all of the measurements are obtained objectively by the algorithm so multiple runs should not produce different results).

For volume measurements for each analyte for each site (i.e. neck and leg), we will plot the value measured by histopathology vs. the difference between the value measured by vascuCAP™ and the value measured by histopathology. Any analyte not measurable will also be indicated on the plot using a different plotting character. The resulting plot will be inspected visually for the following:

1. Limits of vascuCAP™'s quantitation;
2. Associations between the magnitude of the histopathology measurement and bias; and
3. Associations between the magnitude of the histopathology measurements and heteroscedasticity in the vascuCAP™ measurements.

If the plots of carotid and femoral endarterectomies have similar distributions, then the data from these sites will be pooled; otherwise, separate analyses will be performed.

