A linear model will be fit (for all of the data or for a subset of histopathology values, depending on the findings from the plot) where the dependent variable is the vascuCAP™ measurement ( $X$ ) and the independent variable is the histopathology value ( $Y$ ). Generalized estimating equations (GEEs) (to account for the fact that some patients will have more than one target lesion) will be used to estimate the linear function:  $E(Y|X) = \beta_0 + \beta_1 X$ . An unstructured working covariance will be used. We will construct a 95% CI for the intercept  $\beta_0$  using a t-statistic as the pivotal statistic. CIs not containing 0 indicate fixed bias. We will also construct a 95% CI for the slope  $\beta_1$ . CIs not containing 1 indicate proportional bias [11].

The precision of the vascuCAP™ measurements will be estimated by the standard deviation:

$$\sqrt{\frac{1}{n-1} \sum_{i=1}^n (Y_i - X_i - \bar{d})^2} \text{ where } \bar{d} \text{ is the sample mean of the differences, } \bar{d} = \frac{1}{n} \sum_{i=1}^n (Y_i - X_i) \text{ [1].}$$

We will construct a 95% CI for the precision using bootstrap methods.

We will plot the bias profile (plot of bias of measurements for various ranges of histopathology values vs. the histopathology value) and precision profile (plot of standard deviation of vascuCAP™ measurements from patients with similar histopathology values vs. the histopathology value) as visual summaries of vascuCAP™ performance for the bias and precision components, respectively [12].

In addition to reporting these technical performance characteristics of the volume measurements, we will also report i) the coverage probability (CP) and ii) a discrimination index [11]. The CP is the probability that the absolute difference between the value measured by vascuCAP™ and the value measured by histology is less than  $d_0$ , i.e.  $\pi = \Pr(|Y - X| < d_0)$ . We will plot the CP for a range of values for  $d_0$ . The discrimination ability of the measurements, i.e. the ability of vascuCAP™ to discriminate between different magnitudes of histopathology values, will be measured using the area under the ROC curve for continuous measures [13]. 95% CIs for the CP and ROC area will be constructed using methods for clustered binary data [14] and clustered ROC data [15], respectively.

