The volume measurements are considered the most critical because they will be used to construct a score to predict rupture risk. Thus, we considered the width of 95% confidence intervals for the bias and the between-subject variance as a function of sample size (see Tables 1 and 2). The following assumptions were made: 1) the volume measurements are normally distributed; 2) carotid artery patients contribute one target lesion each, while PAD patients contribute two target lesions each; 3) target lesions from the same patient are moderately correlated ( $r=0.5$ ); 4) one-quarter of all patients will be PAD patients; 5) results from femoral and carotid target lesions can be pooled; 6) the average volume of an analyte is  $25\text{mm}^3$ ; and 6) the precision of the vascuCAP™ measurements is 10-20% of the volume of analyte.

From Table 4, if the SD was 15% of the mean volume, then we expect to be able to construct a 95% CI for the bias of total width of 10% with  $n=35$ . If the SD was 20%, then with  $n=35$  we expect to construct a 95% CI of total width of 14%. Similarly, from Table 5, if the SD was 15% of the mean volume, then with  $n=35$  we expect to be able to construct a 95% CI for the precision of total length 8%; if the SD was 20%, then we expect to be able to construct a 95% CI for the precision of total length 11%. We plan to recruit 75 patients (55 carotid artery patients and 20 PAD patients) in phase one to account for the fact that the estimates of bias and

precision may need to be reported in strata based on the magnitude of the histopathology volume and/or by anatomic location. In phase two we plan to recruit at least the minimum of 35 (25 carotid artery patients and 10 PAD patients) and possibly more depending on the results of the training set.

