**Table 4: Width of 95% CIs for Bias Based on Total Sample Size (n)\***

	n=10	n=20	n=30	n=40	n=50	n=60
SD=2.5 (10%)	$\pm 1.72$	$\pm 1.12$	$\pm 0.90$	$\pm 0.77$	$\pm 0.68$	$\pm 0.62$
SD=3.75 (15%)	$\pm 2.58$	$\pm 1.69$	$\pm 1.34$	$\pm 1.15$	$\pm 1.02$	$\pm 0.93$
SD=5.0 (20%)	$\pm 3.44$	$\pm 2.25$	$\pm 1.79$	$\pm 1.54$	$\pm 1.37$	$\pm 1.24$

\*The effective sample size,  $m$ , is calculated as  $m=(3/4)n+(1/4)n(2/[1+(s-1)0.5])$ , where  $s=2$ .

Then the half-width of the 95% CI for bias is  $t_{(m-1),\frac{\alpha}{2}} (SD/\sqrt{m})$ .

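### Section 8.1 contradicts itself on the Aim I bias regression: the words put vascuCAP as the response, but the GEE equation, under the labels given, puts histopathology there

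*Combined protocol and SAP*

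**What the plan says.** Section 8.1 (Aim I) describes the volume regression in two adjacent sentences.

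- The words: "the dependent variable is the vascuCAP™ measurement ( $X$ ) and the independent variable is the histopathology value ( $Y").
- The equation to be estimated by GEE: "E(Y|X) = \beta_0 + \beta_1 X".

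The bias rules are then tied to the two coefficients. A 95% CI for the intercept that misses 0 signals fixed bias, and for the slope "CIs not containing 1 indicate proportional bias".

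Other parts of section 8.1 bear on the intended direction:

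- The first Aim I plot sets the histopathology value against "the difference between the value measured by vascuCAP™ and the value measured by histopathology".
- The bias profile is a "plot of bias of measurements for various ranges of histopathology values vs. the histopathology value", and the precision profile is also set on histopathology.
- The precision formula uses Y − X, where d-bar "is the sample mean of the differences".

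Section 3.1 names histopathology as the ground truth for these analytes. Section 8.2 (Aim II) defines its own symbols and there uses X for vascuCAP and Y for the radiologists.

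**The concern.** The two sentences cannot both be followed. With X as vascuCAP and Y as histopathology, an equation for the mean of Y given X makes histopathology the response, which the sentence before it says is the independent variable. No other section resolves this.

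The direction matters because intercept 0 and slope 1 describe an unbiased device only when the device reading is regressed on an error-free reference. In the other direction, device error sits in the regressor. The slope of an unbiased device is then pulled below 1 and its intercept above 0.

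These two CIs are the only rules that section 8.1 gives for calling bias. They serve primary objective I, for the volume measurements that the plan ranks as most critical. Sections 4 and 8 say that phase-two results go into the 510(k) application.

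**Working it through.** **Which direction is meant.**

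| Element of the plan | Direction it supports |
|---|---|
| Dependent and independent roles in words | vascuCAP on histology |
| Data subset chosen by histopathology value | vascuCAP on histology |
| Bias and precision profiles set on histopathology | vascuCAP on histology |
| Histopathology as ground truth (section 3.1) | vascuCAP on histology |
| GEE equation under the labels given | histology on vascuCAP |

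Only the equation, read through the two letters, points the other way. Two repairs remove the conflict:

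1. Exchange the labels (Y = vascuCAP, X = histology). The equation then agrees with the words, and Y − X becomes vascuCAP minus histology, as in the first Aim I plot.
2. Keep the labels and write E(X|Y) = β0 + β1Y. This matches the use of X in section 8.2, but Y − X in the precision formula is then histology minus vascuCAP and needs its order changed.

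Both give the same model.

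**Inputs for sizing the consequence.** From section 8.1: mean volume 25 mm³; precision stated as "the precision of the vascuCAP™ measurements is 10-20% of the volume of analyte", of which the middle value is used here, 15% or 3.75 mm³; minimum phase-two n = 35. The between-lesion CV is not in the documents. I assume 50% (SD 12.5 mm³) and range it from 30% to 100%.

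**The plan's own figure first.** The footnote to Table 4 gives effective size m = (3/4)n + (1/4)n × 2/[1 + 0.5].

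- n = 30: m = 32.5, and t × 3.75/√32.5 = 1.34, as tabulated.
- n = 35: m = 26.25 + 11.67 = 37.9, and the half-width is 2.026 × 3.75/√37.9 = 1.23 mm³. The total width is 2.47/25 = 9.9%, agreeing with the 10% in the text.

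This is the CI of a mean difference, so it does not depend on regression direction.

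**If the equation were coded with the labels given.** Take an unbiased device and error-free histology.

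- Expected slope = σ²(true) / [σ²(true) + σ²(device)] = 156.25/(156.25 + 14.06) = 0.917.
- Expected intercept = 25 × (1 − 0.917) = 2.1 mm³.

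Share of trials in which the slope CI excludes 1 (OLS, independent lesions, normal volumes, 20,000 trials per setting):

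| Assumed CV | Slope, reversed | False flags, reversed, 38 lesions | False flags, reversed, 81 lesions (n = 75) | False flags, worded direction |
|---|---|---|---|---|
| 30% | 0.80 | 82% | 99% | 5% |
| 50% | 0.92 | 42% | 75% | 5% |
| 100% | 0.98 | 14% | 26% | 5% |

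At CV 100%, about 16% of normal volumes would be negative, so that row is only indicative.

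**If histology also has error** (SD assumed; CV 50%, 38 lesions):

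| Histology SD (mm³) | False flags, worded direction | False flags, reversed |
|---|---|---|
| 0 | 5% | 42% |
| 1.25 | 6% | 39% |
| 2.5 | 10% | 30% |
| 3.75 (equal to device) | 23% | 23% |
| 5.0 | 45% | 18% |

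The reversed direction does worse only while histology error is smaller than device error.

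**What does not change.** The precision SD and Pr(|Y − X| < d0) are symmetric in X and Y. Only the sign of d-bar depends on the labels.

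**The case against.** The strongest reply is that this is a slip of two letters and not a choice of analysis. The roles are named in words, and everything else in section 8.1 is conditioned on histopathology. Harm would require a programmer to follow the letters over the stated roles, and nothing in the documents suggests that anyone would. This stands, and it is why the point is minor.

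The figures also rest on a between-lesion CV that the plan does not give. They run from 14% to 82% at 38 lesions, so they show the direction of the effect better than its size. They come from OLS on independent lesions. A clustered GEE check pointed the same way, but its rate in the correct direction was already 9–10% because the robust SE had no small-sample correction, so it should not be read against 5%.

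A reader might infer that the plan regresses in the wrong direction and will over-call bias. The documents do not support that: on the likeliest reading the intended model is the worded one, and the slip causes no over-flagging. A reader might also infer that the letters in section 8.1 are certainly the mistake. Section 8.2 uses X for vascuCAP, so the equation could equally be what needs turning round.

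What remains is that the equation and the sentence before it disagree, and no other text settles which to code.

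**Conclusion.** Wrong as written; minor. The contradiction is certain from the text and needs no assumption. That it is a notation slip is very likely but not proven.

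The consequence is conditional on literal coding of the labels. In the central case an unbiased device would show a slope of about 0.92, with about 42% false proportional-bias calls against 5%. That case assumes 38 effective lesions, device SD 15%, a between-lesion CV of 50% and error-free histology. With equal errors the direction makes no difference, and with larger histology error the ordering reverses.

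A reader might go further and conclude that the sample size or the other Aim I results are compromised. They are not. Table 4 sizes the study on a mean-difference CI, and precision, coverage probability and the plots do not depend on the regression direction. That mean-difference CI is a planning quantity, however. Section 8.1 does not clearly promise it as a reported result, so it cannot be relied on to correct a misdirected regression. No pass/fail limit is attached to the intercept and slope CIs.

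**What to change.** In section 8.1, state the model once in words and symbols: E(vascuCAP | histology) = β0 + β1 × histology, with the same GEE and the same CI rules. Get there in either of two ways:

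- exchange the two labels in the sentence that names the variables; or
- keep them and write E(X|Y) = β0 + β1Y, which matches section 8.2.

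Define the difference in the precision formula as vascuCAP minus histology, and use one notation across sections 8.1 and 8.2. The cost is a few characters and one line of definitions. No new data are needed, and the sample size is unaffected.

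### The Aim I bias regression sets an unstructured working covariance for unordered lesions and no small-sample variance correction, with perhaps only 35 patients (10 if femoral is analysed alone)

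*Combined protocol and SAP*

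**What the plan says.** Section 8.1 (Aim I) regresses the device volume on the histopathology volume for each functional analyte. It uses GEE "to account for the fact that some patients will have more than one target lesion", and adds: "An unstructured working covariance will be used".

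The intercept gets a 95% interval "using a t-statistic as the pivotal statistic". For the slope the text says only "We will also construct a 95% CI for the slope", with no pivot. The intervals are read as bias verdicts: "CIs not containing 0 indicate fixed bias", and a slope interval that excludes 1 indicates proportional bias.

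The section does not say whether the variance is robust or model-based, whether it is corrected for few patients, which degrees of freedom apply, how lesions are ordered, or what happens if the fit fails.

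On lesion counts there are two statements. The descriptive text expects that "some patients, especially the PAD patients, will have two target lesions, on average". The sample-size assumptions are firmer: "carotid artery patients contribute one target lesion each, while PAD patients contribute two target lesions each". They add that "target lesions from the same patient are moderately correlated", with r=0.5.

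Phase two, which supplies the 510(k) data, has a minimum of 35 patients (25 carotid, 10 PAD). If the carotid and femoral plots differ, the sites are analysed separately.

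**The concern.** There are two separate issues.

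**Working covariance.** An unstructured form gives each pair of lesion positions its own parameter. That suits ordered repeated measures. Lesions have no natural first, second and third, so once a patient has three or more, the parameters depend on how someone numbered them. Each also rests on few patients.

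**Variance.** The usual GEE sandwich standard error is too small when there are few clusters. Here the clusters are patients: 35 at the phase two minimum, 10 if femoral stands alone. A t pivot helps but does not remove the shortfall.

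Aim I is a primary objective. An interval that is too short flags fixed or proportional bias in an unbiased device. A fit that fails without a stated fallback leaves the remedy to be chosen after the data are seen.

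**Working it through.** **Inputs from section 8.1.** r=0.5; SD 3.75 mm³ (15% of a 25 mm³ mean, the middle row of Table 4); one lesion per carotid and two per PAD patient; 75 patients in phase one (55 carotid, 20 PAD) and at least 35 in phase two (25 and 10).

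**Assumptions not in the documents.** True volumes normal with CV 50%; lesion mixes for the case of three or more lesions.

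**Step 1: the plan's own figure.** Table 4 uses m = (3/4)n + (1/4)n × 2/1.5 = 1.083n and half-width t × SD/√m. At n=30, m=32.5 and the half-width is 1.34, as stated. With m−1 degrees of freedom every cell reproduces within 1.4%. Table 4 concerns a mean difference, however. The plan gives no coverage figure for the GEE intervals, so that has to be simulated.

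**Step 2: size of the unstructured matrix.** With at most s lesions there are s(s−1)/2 correlations.
- s=2 gives one. Under a common scale this is the exchangeable model, and relabelling changed nothing in simulation.
- If variances also differ by position, relabelling moved estimates by a median of 0.003-0.018 SE and changed 0.7-4% of verdicts.
- s=3 gives three. Take ten patients with 1,1,1,2,2,2,2,3,3,3 lesions (mean 20/10 = 2.0). The first correlation rests on 4+3 = 7 patients and the other two on 3 each.

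**Step 3: coverage with at most two lesions.** The model was Gaussian GEE with true intercept 0 and slope 1, and t on K−2 degrees of freedom (K patients). There were 1,500-3,000 runs per main setting, so the 95% Monte Carlo margin at 92% with 1,500 runs is 1.96 × √(0.92×0.08/1500) = 1.4 points. Entries are intercept/slope coverage in %.

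| Fit | K | Sandwich, z | Sandwich, t | Mancl-DeRouen, t |
|---|---|---|---|---|
| Femoral, phase two minimum | 10 | 83/81 | 88/87 | 94/93 |
| Femoral, phase one | 20 | 89/89 | 91/91 | 94/94 |
| Carotid, phase two minimum | 25 | 91/90 | 93/92 | 95/95 |
| Pooled, phase two minimum | 35 | 91/91 | 92/92 | 94/94 |
| Pooled, phase one | 75 | – | 94/94 | 95/95 |

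A separately coded simulation with t gave 91/89 (10 femoral) and 93/91 (35 pooled). Together the ranges are about 87-91% and 91-93%. A 300-run check in statsmodels gave 88/88 and 91/89, with a margin of 1.96 × √(0.89×0.11/300) = 3.5 points.

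Sensitivity, uncorrected with t: lognormal volumes gave 90/85 (10 femoral) and 92/90 (35 pooled). SD proportional to volume gave 81/74 and 87/84.

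**Step 4: false flags.** Coverage of 91-93% means 7-9% false flags per interval instead of 5%. Over six analytes and two intervals each, an unbiased device expects 12 × 0.05 = 0.6 flags at nominal level, and 12 × 0.07 to 12 × 0.09 = 0.84 to 1.08 with 35 pooled patients.

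**Step 5: fit failure** (no convergence, or a correlation matrix that is not positive definite).
- At most two lesions, r=0.5: 0.1-2% (10 femoral), 5-16% (35 pooled), 1-4% (75 pooled). At r=0.8, 22-45% for 35 pooled. Under a common scale exchangeable is the same model here and gives no relief.
- A few patients with three lesions: 36-46% unstructured, against at most 8% exchangeable.
- A mix of one to four lesions: 74-80% unstructured, 3-18% exchangeable, 0% independence. Among unstructured fits that worked, relabelling moved estimates by 0.4-1.1 SE at the 95th percentile and changed 2-11% of verdicts. Only 62-108 relabelled pairs could be compared per setting, so these figures are rough.

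**The case against.** The strongest reply is that the plan never says it will use an uncorrected robust variance. It is silent on the estimator, and its t pivot for the intercept is already a partial small-sample allowance. That is right, so the coverage figures are conditional on the usual GEE default. But the t pivot is not enough: the 87-93% figures already include it.

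A second reply is that the planning case has at most two lesions, where unstructured is harmless. This also stands. A reader might infer from the words on lesion averages that some patients will have three or more, and that renumbering lesions will change the answer. The documents do not support that. The averages phrase is loose, the sample-size assumptions and the Table 4 and 5 footnotes use two, and no patient with three is described. Three or more is only not ruled out.

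Third, 35 is a minimum. Section 4 allows up to 75 in phase two, and the 10-patient fit arises only at the minimum and without pooling. At 75 pooled patients uncorrected coverage is about 94%. A carotid-only fit with one lesion each has no correlation to estimate, so only the variance issue applies there.

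Finally, Aim I is estimation without a pass/fail limit, and the intervals stand beside precision, coverage probability and ROC area. That limits the consequence, but the plan still reads the intervals as indicating bias.

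**Conclusion.** The point holds as a worthwhile and cheap improvement. Given the usual sandwich variance, constant SD, r=0.5 and an assumed volume CV of 50%, nominal 95% intervals cover about 91-93% with 35 pooled patients and about 87-91% with 10 femoral patients using t. They cover less with z, and less again if SD grows with volume.

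The unstructured form does real damage only if some patients have three or more lesions. Failure is then roughly 40% or more, depending on the mix, and results depend on numbering. Under the planning assumption of at most two lesions it makes little or no difference, though a pooled 35-patient fit can still fail with no stated fallback.

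A reader might infer coverage as low as 84% as a general figure. One simulation did give that, but it needed unpooled sites, only 10 PAD patients and an assumed mix of one to three lesions together. The documents support none of these as the expected case.

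**What to change.** In section 8.1, replace the unstructured working covariance with an exchangeable working correlation under a common scale. Prespecify independence as the fallback if the fit does not converge or the correlation matrix is not positive definite. The fallback is needed even with two lesions, where exchangeable can fail as unstructured does.

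For both the intercept and the slope, state a small-sample bias-corrected sandwich variance (for example Mancl-DeRouen) and a t pivot with degrees of freedom from the number of patients (for example patients minus 2).

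This restores coverage to about 93-95% under constant SD. It was not evaluated for SD that grows with volume. The cost is a few sentences in the SAP and slightly wider intervals. No extra patients or data are needed, and Tables 4 and 5 do not rest on the GEE.

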#### 4 STUDY DESIGN

A two-phase study is proposed. In the first phase, 75 surgical patients will be recruited as part of a training set; aims I-II will be evaluated with this set. In the second phase, at least a minimum of 35 and as many as 75 surgical patients will be recruited (number to be set based on the results of a statistical analysis following the first phase). Data from the second phase will be used in the definitive results to be filed in a 510(k) application to the FDA documenting the statistical performance of vascuCAP™'s ability to measure functional and structural analytes according to Aims I and II. Data collected in the second phase will also be used as additional training data for Aim III.

vascuCAP™'s performance in measuring functional analytes will be assessed using histology of specimens collected during surgery as ground truth. vascuCAP™'s performance in measuring structural analytes will be facilitated by comparing its automated segmentations against manual contours produced independently by two radiologists recruited for the study. The two radiologists will independently perform the manual contouring for all study patients, and one of these two radiologists will also perform the vascuCAP™ aided contouring after a sufficient wash-out period after the manual contouring and with appropriate blinding to their manual results.

Patients are recruited, enrolled, and analyzed with vascuCAP™. 75 patients which have been imaged and on which surgery was performed within 30 days of imaging will form the training set. An analysis will be performed and revisions to vascuCAP™ will be made, as appropriate. The sample size for the *Profiling* will be determined at this time; we denote this as  $N_{\text{profile}}$ . After analysis, the product configuration will be locked, and subsequent patient results are blinded. After  $N_{\text{profile}}$  additional patients have been imaged and on which surgery was performed within 30 days of imaging ( $N_{\text{profile}} \geq 35$ ).

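### Aim I calls overall volume bias only when the intercept CI excludes 0 or the slope CI excludes 1; no tolerable bias is set, and the intercept CI is much wider than the mean-difference CI that Table 4 sized

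*Combined protocol and SAP*

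**What the plan says.** Estimating bias against histopathology is a primary objective (section 3.1), and section 8.1 calls the volume measurements the most critical. For these, section 8.1 fits a linear model by GEE, forms a 95% CI for the intercept "using a t-statistic as the pivotal statistic", and forms one for the slope. It attaches a label to each: "CIs not containing 0 indicate fixed bias" and "CIs not containing 1 indicate proportional bias". No other rule for calling overall volume bias is given, and no tolerable bias appears anywhere.

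The section describes the model in two ways. In words it is one "where the dependent variable is the vascuCAP™ measurement" (called X) and histopathology (Y) is the independent variable. The printed equation is "E(Y|X) = \beta_0 + \beta_1 X", which regresses histopathology on the device.

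The sample size in section 8.1 and Table 4 rests on the CI for a mean difference. Phase two has at least 35 patients (25 carotid, 10 PAD), and section 4 says "Data from the second phase will be used in the definitive results to be filed in a 510(k) application to the FDA".

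**The concern.** A CI that contains 0 or 1 may do so because bias is small or because the CI is wide. With no tolerable bias, the rule cannot tell these apart. An intercept CI can be very wide: it estimates the device reading at a histology volume of zero, which may lie far from most of the data. The precision quoted in Table 4 therefore need not apply to the CI that drives the label. At stake is how the bias results in the 510(k) submission are read. In the other direction, a large enough sample would flag a bias too small to matter.

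**Working it through.** **Inputs from section 8.1.** 25 carotid patients with one lesion and 10 PAD patients with two; correlation 0.5 between lesions in a patient; mean volume 25 mm³; SD 10%, 15% or 20% of the mean (2.5, 3.75, 5.0 mm³).

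**Assumptions, because the plan gives no figure.** CV of histology volume of 30%, 50% or 80% (S = 7.5, 12.5, 20 mm³), lognormal. Illustrative bias of 2.5 mm³, which is 10% of the mean.

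**Step 1: reproduce the plan's figure.** Effective size m = 0.75n + 0.25n(2/1.5). At n=35, m = 37.9. Half-width = t × SD/√m. With t on n−1 df, Table 4 reproduces to within 0.01.
- SD 15%: 2.03 × 3.75/6.16 = 1.24 mm³. Total width 2 × 1.24/25 = 9.9%; the plan says 10%.
- SD 20%: 1.65 mm³, total width 13.2%; the plan says 14%, slightly wide.

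**Step 2: the CI the rule uses.** With the device regressed on histology, SE(b0) = SD × √[1/m + 25²/((m−1)S²)]. At SD 15%, with t = 2.03 on 33 df:
- CV 30%: 3.75 × √(0.026 + 0.301) = 2.15; half-width about 4.4 mm³
- CV 50%: 3.75 × √(0.026 + 0.108) = 1.38; half-width about 2.8 mm³
- CV 80%: 3.75 × √(0.026 + 0.042) = 0.98; half-width about 2.0 mm³

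Simulating the clustered design (volumes and errors both correlated 0.5 within patient, generalised least squares fit) gives about 4.1, 2.7 and 2.0 mm³, roughly 3.3, 2.2 and 1.6 times the Table 4 value.

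**Step 3: how often a constant 2.5 mm³ bias is missed by both CIs** (simulation, n=35, device on histology):

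| SD | CV 30% | CV 50% | CV 80% |
|---|---|---|---|
| 10% | 54% | 20% | 4% |
| 15% | 73% | 53% | 29% |
| 20% | 85% | 68% | 49% |

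Other fitting choices move these by a few points. At CV 50% and SD 15%, an independence working model with robust standard errors misses 50%, and a separate generalised least squares run misses 46%.

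**Step 4: the alternative on the same data.** The fitted bias at histology volume h is b0 + (b1−1)h. At the mean volume its SE is close to SD/√m, the Table 4 quantity. A 2.5 mm³ bias is then 2.5/(SD/√m) = 6.2, 4.1 or 3.1 standard errors at SD 10%, 15% or 20%. By the noncentral t, its CI excludes 0 in about 100%, 98% and 85% of trials. A 10% proportional bias is also 0.10 × 25 = 2.5 mm³ at the mean volume.

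**Step 5: regression direction.** Under the printed equation, noise in the device attenuates the slope (to about 0.96, 0.91 and 0.85 at SD 10%, 15% and 20%, CV 50%). A device with no bias is then flagged in about 33%, 53% and 71% of trials.

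**The case against.** Aim I is an estimation aim with no pass or fail test. Beyond the two CIs, section 8.1 reports the SD with a bootstrap CI, bias and precision profiles, an ROC-type index and coverage probability. Noise or bias would generally show in several of these. This stands, and it limits the harm. But none of these outputs carries a threshold. For coverage the plan says only "We will plot the CP for a range of values for" the allowed difference. The later F and Wald tests ask whether site, scanner, field strength or patient characteristics predict bias, not whether bias is acceptable.

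A reader might infer three stronger things, which the documents do not support.
- **That an unflagged analyte will be declared unbiased.** The plan never says so; it is silent on how to read such a CI.
- **That a relevant bias will usually go unflagged with 35 patients.** The plan defines neither a relevant bias nor the spread of volumes. At SD 10%, which is within the plan's range, a 2.5 mm³ bias is missed in only 20% (CV 50%) or 4% (CV 80%) of trials. A 20% bias is flagged in most of the settings examined. Also, 35 is a floor: section 4 allows up to 75.
- **That a noisier device is more likely to look unbiased.** This holds for the regression as worded and reverses under the printed equation.

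**Conclusion.** The point holds in this form: the only rule for calling overall volume bias has no tolerable bias behind it, a CI that contains 0 or 1 is not evidence that bias is small, and the intercept CI is much wider than the CI on which the sample size rests. A 10% constant bias may often go unflagged at SD 15–20%: 29% to 85% missed over the CVs examined, against about 2% and 15% missed by a CI for the fitted bias at the mean volume. These figures rest on the plan's planning values, n=35, the device regressed on histology, and an assumed CV and shape for histology volumes. Under either regression direction the label depends on noise and volume spread, and does not answer whether bias is acceptably small.

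**What to change.** 1. Reconcile the wording and the equation in section 8.1, so that it is clear which variable is regressed on which.
2. Keep the intercept and slope CIs, but draw the bias conclusion from the estimate and 95% CI of b0 + (b1−1)h at low, mean and high histology volumes h fixed in advance (device regressed on histology). State that a CI containing 0 or 1 is not evidence of no bias.
3. If negligible bias is to be claimed, fix a tolerable bias per analyte before phase two is unblinded. The lock of the product configuration after phase one (section 4) is a natural moment. Require the CI at the mean volume to lie inside that limit, and report any other result as inconclusive.

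Items 1 and 2 cost only SAP wording. Item 3 needs one justified limit per analyte and no extra patients, but some unbiased analytes will be reported as inconclusive. With an illustrative limit of 2.5 mm³ and n=35, an unbiased device meets it at the mean volume in about 95% (SD 15%) or 70% (SD 20%) of trials. Requiring it at all three volumes (mean and mean ± 1 SD of histology volume) lowers this to about 40% or 5%, so the low and high volumes should be descriptive.
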